4.2.2 SECONDARY ENDPOINTS

1) Quality of life as measured by Kansas City Cardiomyopathy Questionnaire 2) Cost effectiveness analysis between the two arms at 30 days.

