7.3.3 FOLLOW-UP & FINAL STUDY VISIT

Patients will have follow up at 30 (+/- 7 days) days and 90 (+/- 30) days post-discharge (up to 120 total days after randomization is allowed if difficult to get a hold of a patient or more time is required to complete forms). There will be NO further in-person visits once discharged. However, treatment during hospitalization will be recorded. Patients will be called 30 days post-discharge ((+) 7 business days) and 90 days post-discharge (+/- 30 days) to assess vital status, re-hospitalizations or ED visits, as well as quality of life, caregiver burden, and resource utilization.

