Decreasing hospital stays may increase caregiver burden. Thus, we will also assess caregiver burden, using both the Oberst Caregiver Burden and Bakas Caregiver Outcome Scales, both validated instruments prior to discharge and again at 30 days.⁶⁸ Other measures of caregiver burden in HF have either not involved input from actual caregivers or missed important conceptual domains.⁶⁸ Effective caregivers has been associated with improved quality of life, lower hospitalization rates, and reduced mortality.^{68,69} As our primary focus is on the patient, the eligibility criteria for the caregiver will be broad, essentially including any person who after separate written informed consent, acknowledges themselves as the primary caregiver for the patient.

Out-of-pocket costs directly impact patients. As such, we will assess healthcare utilization from a societal perspective using the Modified Resource Utilization Questionnaire for Heart Failure (mRUQ-HF).⁷⁰ The mRUQ-HF is a 14-item self-report questionnaire of comprehensive lists of choice related to healthcare utilization. (See Appendix trial protocol) Exploratory analysis will occur in two steps: 1) Determination of resources consumed or related; 2) Assignment of 'value' to the resources consumed.⁷¹ This two-step process allows for transparency of assigned costs. Hospital costs will be assigned per individual hospital cost-accounting. Where monetary values are not directly self-reported, Medicare fee schedules will be used for uniformity.

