Here, E_{SSU} and C_{SSU} are the effectiveness and cost, respectively, of the SSU, while the E_H and C_H are the effectiveness and cost of the hospital admission. The incremental cost effectiveness ratio allows us to estimate the additional cost associated with SSU treatment proportionate to the increased effectiveness of its patient outcome. We expect SSU treatment to dominate hospital admission, resulting in greater effectiveness at a lower cost.^{1,2} Therefore, we expect ICER to be negative, reflecting the cost savings of implementing SSU treatment.

Our goal is to evaluate the cost-effectiveness of the SSU strategy from a societal perspective, as we will account for the costs of care from both the hospital/insurer perspective and patient point-of-view. As discussed in more detail below, our primary challenges lie in obtaining accurate and complete costs incurred by the patient outside of the hospital setting. Given this potential limitation, at minimum, our CEA evaluation will be from the hospital/payer perspective.

We will use an episodic approach to costing, which accounts for any cost shifting to a later point in time. This is the preferred approach for the Centers for Medicaid and Medicare services. Specifically, we will examine the total cost of patient care from the index ED visit (study enrollment) for a period of 30 days. In the context of the episode, we will analyze the incidence of readmission, total days of hospitalization, utilization of outpatient care, total cost, and caregiver burden.

The outcome variables of interest are cost, effectiveness, and other characteristics of participant experience. Costs will be defined by total billable hospital costs (Table 1) and patient costs. Hospital costs include payments by insurance, patients, and third parties. While this type of cost information is most accurate for our purposes, it is also the most difficult to obtain. Recognizing the phenomenon of 'upcharging,' we will obtain hospital charges from each site as this is the easier data to acquire.

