Given the difficulty of obtaining costs and payments, we will standardize hospitalization and SSU costs using Medicare reimbursement rates (See Sensitivity Analysis Section below). Patient costs will include self-reported out-of-pocket costs and time costs using a modified version of a previously published survey. (see attached) One limitation of self-reported data will be potential mismeasurement due to recall bias. Should the patient-completed survey lack a sufficient response rate for outpatient analysis, we will limit our analysis to the hospital portion of the treatment. Effectiveness will be defined by SF-12 and SF-6D metrics of patient self-reported QOL. The SF-12 has been previously used to evaluate outcomes for HF patients.³ Effectiveness in ICER computations is often measured using quality-adjusted life years (QALYs), defined as:

$$QALY = \sum_{t=t_0}^Z \delta^{t-t_0} q_t P_t$$

where P_t is the probability of surviving to each year t , q_t is the preference weight, and δ is the time-discounting factor. As the SF-12 does not allow direct assessment of QALYs, we will convert the score into a SF-6D preference based score using the six health dimension scores from the SF-12^{4,5} to generate the preference weights and probabilities necessary to conduct the cost-utility analysis. Since the participant will be completing the SF-12 survey at the beginning and end of the episode, all models estimating the effectiveness will include the baseline score in the vector of participant characteristics. Aside from cost and effectiveness, we will analyze the incidence of re-admission, the utilization of outpatient care, and caregiver burden, as detailed in our statistical analysis plan. While the incidence of re-admission will be obtained from both the electronic health record and patient self-report, the outpatient and caregiver burden are self-reported.

For each outcome variable of interest (patient costs, hospital costs, total episode costs, SF-12 scores, SF-6D scores, QALYs, incidence of readmission, total days of hospitalization, utilization of outpatient care, nursing care, and caregiver burden) we will estimate a predictive model accounting for the heterogeneity among participants in the intervention and control groups.

$$Y_i = \alpha + \beta_1 SSU_i + \beta_2 D_i + \beta_3 R_i + \beta_4 D_i * R_i + \beta_5 D_i * SSU_i + \beta_6 R_i * SSU_i + \beta_7 D_i * R_i * SSU_i + \gamma X_i + \delta H_h + \kappa_h + \tau_t + \varepsilon_i$$

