Intervention Monitoring: To ensure fidelity of each component of the intervention between study arms, we will also measure the following individual components of the intervention throughout the trial at both the site and overall study level: 1) Baseline patient characteristics, 2) Medicine reconciliation 3) Guideline-HF adherence 4) SSU AHF protocol adherence, 5) admission rates from the SSU 6) Quality of Life/Caregiver Burden Questionnaire response and completeness, 7) Hospitalized patients discharged within 48 hours, and 8) Follow up completed at 30 days. These analyses will be reported every 3 months to the Steering Committee to allow for course correction as needed. In addition, these will be reported at the conclusion of the study as well as at quarterly enrollment milestones to the DSMB.

Sensitivity Analyses: Some baseline covariates such as co-morbidities, medications, renal function, serum sodium, potassium, b-type natriuretic peptide (BNP) or NT-pro BNP, and blood pressure, may not be well-balanced between the two arms despite randomization. These covariates are known markers of risk in AHF patients and are part of the standard assessment for the vast majority of AHF admissions. We will use the inverse probability weighting approach to adjust those covariates with poor balance between the arms as part of a sensitivity analysis.⁷⁵ We will then compare these results with those from the two-sample t test. In addition, if the DAOOH, QoL, caregiver burden, or mRUQ-HF endpoints are found to be non-normal in distribution, the Wilcoxon Rank-Sum test will be used for comparison as a sensitivity analysis.

Modified Resource Utilization Questionnaire for Heart Failure (mRUQ-HF).⁷⁰ The mRUQ-HF is a 14-item self-report questionnaire of comprehensive lists of choice related to healthcare utilization. (See Appendix trial protocol) Exploratory analysis will occur in two steps: 1) Determination of resources consumed or related; 2) Assignment of 'value' to the resources consumed.⁷¹ This two-step process allows for transparency of assigned costs. Hospital costs will be assigned per individual hospital cost-accounting. Where monetary values are not directly self-reported, Medicare fee schedules will be used for uniformity. This will be captured at 90 days and will include the hospitalization when patients answer the questionnaire.

All Cause Mortality and All-Cause Rehospitalization Endpoints:

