0 Did Not Change 1

2

3 Changed for the Best

OBERST CAREGIVING
BURDEN SCALE.docxBCOS120715 -
modified HF.doc**17.3 MRUQ-HF**

MODIFIED RESOURCE UTILIZATION QUESTIONNAIRE FOR HEART FAILURE
(SOCIETAL PERSPECTIVE)

This is a series of questions about your health care that you have received during **past 3 months**.

1. During the **past 3 months**, how many times have you had **appointments or visits** at any of the following clinics or providers?

Clinics / Providers	Number of Appointments/Visits	How Long (hours)	Reason for Appointments/Visits
Cardiologist			
Home health services			

Nurse clinic visit			
Emergency department			
Hospitalization			
Other healthcare appointments			
Endocrinologist			
Nephrologist			
Ophthalmologist			
Allergist/Ear Nose Throat clinic			
Alternative/ homeopathic medicine			
Chiropractor			
Dentist			
Dermatologist			
Family physician/ internal medicine/ primary care physician			
Gastroenterologist			
Mental health professional			
Orthopedist			
Physical therapist			
Physician assistant			
Podiatrist			
Other:	—		

2. Not including the visits just listed, during the **past 3 months**, how many times did you communicate (**telephone, e-mail, text, fax**) with anyone (physician, nurse, or technical support) regarding your heart condition?

	Reason for contact	Number of contacts for information needed or communication	Type of communication (phone, e-mail, etc)
Physician			
Nurse practitioner			
Nurse educator			
Social worker			
Technical (e.g., pacemaker company)			

Other:			
--------	--	--	--

3. Within the **past 3 months**, have you been visited in your home for **heart failure education**, attended a class, or a support/informational group? Yes No

3a. If **yes**, how long was each educational session and who participated in the education process with you.

	Purpose	Length of Session	How many times	Who participated with (spouse/child/sibling/other)
Visited at home				
Attended a class				
Heart failure support group				
Other:				

4. Within the **past 3 months**, have you or other family members attended **mental health counseling** sessions for support? Yes No

4a. If **yes**, how long was each counseling session and who participated in the process with you.

	Purpose	Length of Session	Who participated with (spouse/child/sibling/other)
Session 1			
Session 2			
Session 3			
Session 4			

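### Patient costs for the 30-day societal cost-effectiveness analysis appear to come from a 3-month recall survey placed at 90 days, and its totals cannot be cut to the 30-day episode

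*Combined protocol and SAP*

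**What the plan says.** Section 4.2.2 lists as a secondary endpoint: "Cost effectiveness analysis between the two arms at 30 days". Section 10.4.3 fixes the costing period: "we will examine the total cost of patient care from the index ED visit (study enrollment) for a period of 30 days". The same section states the perspective: "Our goal is to evaluate the cost-effectiveness of the SSU strategy from a societal perspective". On patient costs it says: "Patient costs will include self-reported out-of-pocket costs and time costs using a modified version of a previously published survey. (see attached". It does not name that survey. The mRUQ-HF, reproduced in section 17.3 and headed as taking a societal perspective, is the only resource-use survey in section 17. Section 10.1.1 ties it to the patient's own costs: "Out-of-pocket costs directly impact patients. As such, we will assess healthcare utilization from a societal perspective using the Modified Resource Utilization Questionnaire".

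On timing, the sections differ:

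- The synopsis lists the mRUQ-HF as an exploratory measure at 90 days.
- Section 10.4.3.1 says: "This will be captured at 90 days and will include the hospitalization when patients answer the questionnaire".
- Section 7.3.3 describes the calls at 30 and at 90 days together and gives their purpose as "to assess vital status, re-hospitalizations or ED visits, as well as quality of life, caregiver burden, and resource utilization". That reads as collection at both.
- In the schedule (section 7.3.7) the mRUQ-HF row sits in the combined 30- and 90-day column and carries footnote 2, which concerns subject payments. Footnote 3, which restricts an item to 90 days, is attached to no row.

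The questionnaire opens: "This is a series of questions about your health care that you have received during" the past 3 months. Its visit, contact, spending, time and work items keep that period. Insurance premium and deductible are asked as annual figures.

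**The concern.** An ICER needs costs and effects over one horizon. Here hospital costs and QALYs are defined over 30 days, while the self-reported component arrives as an undivided total over about 90 days, with no rule for taking out the 30-day share. The plan has a fallback to hospital costs, but section 10.4.3 links it to incomplete patient cost data or poor survey response. A survey with full response would not trigger the response-rate fallback, and its totals would still have the wrong window.

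The societal element is not incidental. Section 2.2 names possible higher out-of-pocket costs under short-stay care as a knowledge gap that the trial will address.

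**Working it through.** The plan gives no sample size, power or precision for the CEA, so there is no figure of its own to reproduce. The check compares time windows.

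**Inputs**
- Episode: day 0 (index ED visit) to day 30 (section 10.4.3).
- Contact: 90 ± 30 days after discharge, with up to 120 days after randomization allowed (section 7.3.3).
- Index stay: under 24 hours for SSU, taken as 1 day (section 6.1.1); mean 5 and median 4.3 days for usual care (section 10.5).
- Recall: past 3 months (section 17.3), taken as L = 90 to 92 days. This range is an assumption.

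**Formulas**
- Contact day T = index stay + days since discharge.
- Recall window = [T − L, T].
- Episode days covered = max(0, 30 − max(0, T − L)).
- Days before the index visit = max(0, L − T).
- Days after day 30 = T − max(30, T − L).

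Paired results are for L = 90 / L = 92.

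| Contact | Arm (stay) | T | Window opens on day | Episode days covered | Days before index visit | Days after day 30 |
|---|---|---|---|---|---|---|
| 60 days post-discharge | SSU (1) | 61 | −29 / −31 | 30 / 30 | 29 / 31 | 31 |
| 60 days post-discharge | Usual care (5) | 65 | −25 / −27 | 30 / 30 | 25 / 27 | 35 |
| 90 days post-discharge | SSU (1) | 91 | 1 / −1 | 29 / 30 | 0 / 1 | 61 |
| 90 days post-discharge | Usual care (5) | 95 | 5 / 3 | 25 / 27 | 0 / 0 | 65 |
| Day 120 after randomization | Either | 120 | 30 / 28 | 0 / 2 | 0 / 0 | 90 |

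Example, usual care at nominal contact with L = 90: T = 5 + 90 = 95; the window opens on day 95 − 90 = 5; episode days covered = 30 − 5 = 25; later days = 95 − 30 = 65. With the median stay of 4.3 days, coverage is 30 − 4.3 = 25.7 days.

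If 120 days after discharge is allowed without the 120-day limit from randomization, T is 121 to 125 and coverage is 0 to 1 day. Section 7.3.3 permits both readings, and they differ for any stay longer than zero days.

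**What follows**
1. A window of 90 to 92 days can never equal one of 30 days. Even when the whole episode is inside, it is about a third of the period recalled (30/90 = 33%).
2. At nominal contact with L = 90, recall opens on the day of discharge, so the index stay falls outside it: 1 day for SSU, 4.3 to 5 days for usual care. With L = 92, the SSU day is inside and 2 of the 4.3 to 5 usual-care days are.
3. Reading section 7.3.3 as collection at both calls does not solve this under the printed wording. At a call 30 days after discharge, T is 31 to 35, so the window opens between day 31 − 92 = −61 and day 35 − 90 = −55. It covers the episode but adds 55 to 61 days before enrolment.

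**The case against.** The case for treating this as a minor clarification has real substance.

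- **The survey is not named.** Section 10.4.3 refers only to an attached survey. That it is the mRUQ-HF is a strong inference, not a stated fact. Section 17 is not exhaustive (the SF-12 is not reproduced there), and the mRUQ-HF analysis is called exploratory. This stands as a caveat.
- **Collection only at 90 days is not certain.** Section 7.3.3 points to both calls, and the schedule footnote is probably a numbering slip. This stands too, but the printed recall wording fails at either call.
- **A reader might infer that the survey misses the episode altogether.** That holds only for contact near day 120. At nominal timing most of the episode is inside the window. Section 10.4.3.1 also says that the hospitalization will be included, although no item anchors recall to it.
- **A reader might infer that patient cost is three times too large.** The ratio 90/30 = 3 compares time windows, not money. No section instructs the analyst to add a 90-day total to the 30-day ICER; the gap is a missing rule. The numerator is also a between-arm difference, so later costs that are equal in the two arms would cancel in expectation and mainly add noise. Whether they are equal is not known.
- **A reader might infer that the hospital/payer fallback removes exactly the cost on which SSU may be worse.** The mRUQ-HF does not support that. It asks for visits, hours and reasons, for uninsured spending on equipment and medication, and for annual premium and deductible. It does not ask what the patient paid for the index SSU or hospital stay. Section 10.4.3 places patient payments within hospital costs, through the payments measure in its Table 1.

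The plan also concedes recall bias, guarantees at least a hospital/payer analysis and already contains a 90-day CEA. That limits the damage, but it does not align the windows.

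**Conclusion.** The mismatch holds at every contact date the plan allows. Self-reported patient costs, if taken from the mRUQ-HF as printed, do not cover the same period as the 30-day hospital costs and QALYs and cannot be divided to do so. At nominal timing about 25 to 30 of the 30 episode days are mixed with 61 to 65 later days. The early edge adds 25 to 31 days before enrolment, and the late edge retains 0 to 2 episode days.

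The direction and size of any bias in the ICER cannot be derived from the documents. The conclusion rests on the mRUQ-HF being the survey meant in section 10.4.3, on 3 months being 90 to 92 days, and on the plan's own index stays. Hospital costs, the hospital/payer CEA and the primary endpoint are unaffected, and the 90-day exploratory CEA fits the recall period much better. This should be corrected, because it affects a named secondary endpoint and the remedy is cheap.

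**What to change.** Name the survey in section 10.4.3, then choose one of two routes.

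1. **Collect at 30 days.** Ask the mRUQ-HF cost, visit and time items at the existing 30-day call, with recall running from the index ED visit, and at 90 days with recall running from the previous call. Record the call date: at nominal timing anchored recall spans 31 to 35 days (stay of 1 to 5 days plus 30), so a short rule for trimming to day 30 is still needed. Cost: a few more minutes per call, CRF changes and a change to the questionnaire's printed recall wording.
2. **Change the analysis.** Define the 30-day CEA as hospital/payer only and make the societal CEA the 90-day one already planned, with recall at that call anchored to the index ED visit. State how contacts earlier or later than 90 days are handled, since T runs from 61 to 120 days. Cost: SAP wording and one line in the questionnaire; the societal result at 30 days is given up.

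Under either route, reconcile section 7.3.3, footnotes 2 and 3 in section 7.3.7, and section 10.4.3.1 on when the mRUQ-HF is given. Neither route captures the patient's own bill for the index stay. If the societal analysis is meant to include it, the plan should say which source supplies it.

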10.4.4 SAFETY ANALYSES

As all cause mortality and re-hospitalizations will already be reported as part of the efficacy exploratory analyses, these will also be highlighted as safety analyses. We will also report the proportion of patients who are admitted from the SSU as well as AE/SAE's.

10.4.5 ADHERENCE AND RETENTION ANALYSES

Missing data: This study does not anticipate significant missing data because the follow-up is fairly short. However, we have planned for this unlikely possibility in both our sample size calculations and analysis plan. The magnitude of any missing data and their relevant distributions will be properly documented. Multiple-imputation⁴² will be used to analyze the incomplete data under the assumption of missing at random (MAR).⁴³ If it is of concern that the data may be missing not at random (MNAR),⁴³ then a sensitivity analysis will be performed under multiple imputation scheme.⁴⁴ Summary data at baseline based on subjects with legitimate values on corresponding variables will be reported. For main inferential statistics, results based on the strategy of ignoring the missing data and multiple imputations will be reported so that the impact of missing data can be assessed.

To ensure completeness, medical records will also be reviewed for items such as past medical history, lab results, medications, and other test results. The DCC will perform data audits at periodic intervals to assess the integrity of the data, also checking for missing data. Any fields with more than 5% missing data will be flagged for further investigation, with queries to sites to ascertain the reasons and/or fix accordingly. If needed, protocols or procedures will be implemented, along with further education, to minimize further missing data. In terms of drop-outs, a well-trained study team works to minimize this through careful screening and informed consent. While patients may withdraw their consent at any time, reasons for withdrawal will be queried and tabulated. For patients who drop out, the reason for dropping out will be queried and recorded. These will be tabulated to determine if specific reasons for drop-outs are occurring, which will then be addressed by the Executive Committee. Every attempt to complete assessments for the

outcomes of interest to this study will be undertaken. In keeping with the pragmatic, simple nature of this trial design, there will be no clinical events or adjudication committee, as total DAOOH will be counted, irrespective of mode of death or re-hospitalization.

